3 ELIGIBILITY ASSESSMENT AND ENROLLMENT

3.1 Eligibility Criteria

3.1.1 Inclusion Criteria

- 3.1.1.1 Subject must be ≥ 18 years old.
- 3.1.1.2 Diagnosis
 - Arm 1: Subject must have a documented diagnosis of prostate cancer with evidence of lymph node involvement (with a short axis diameter of ≥1.5cm on a conventional CT or MRI obtained within 8 weeks of the Ferumoxytol imaging procedure)
 - Arm 2: Subject must have a documented diagnosis of bladder cancer (transitional cell carcinoma) with evidence of lymph node involvement (with a short axis diameter of ≥1.5cm on a conventional CT or MRI obtained within 8 weeks of the Ferumoxytol imaging procedure)

- Arm 3: Subject must have a documented diagnosis of kidney cancer (all renal cell cancer types) with evidence of lymph node involvement (with a short axis diameter of ≥1.5cm on a conventional CT or MRI obtained within 8 weeks of the Ferumoxytol imaging procedure)
- 3.1.1.3 Subject must have Eastern Cooperative Oncology Group Performance score ≤ 2 .
- 3.1.1.4 Ability to provide informed consent. All subjects must sign an informed consent form indicating their understanding of the investigational nature and risks of the study before any protocol-related studies are performed.

3.1.2 Exclusion Criteria

- 3.1.2.1 Subjects with known hypersensitivity and allergy to iron
- 3.1.2.2 Subjects with evidence of iron overload with a pre-study ferritin level greater than 370 ng/ml and percent saturation of transferrin level greater than 40%. Patients with lab values above these limits may be included in the study if documented hematology consultation rules out hemochromatosis, idiopathic or iatrogenic iron overload.
- 3.1.2.3 Subjects with any coexisting medical or psychiatric condition that is likely to interfere with study procedures and/or results
- 3.1.2.4 Subjects with severe claustrophobia unresponsive to oral anxiolytics
- 3.1.2.5 Subjects with contraindications to MRI
- 3.1.2.6 Subjects weighing >136 kg (weight limit for scanner table)
- 3.1.2.7 Subjects with any type of pacemaker, cerebral aneurysm clips, shrapnel injury, or other implanted electronic devices or metal not compatible with MRI.
- 3.1.2.8 Subjects with abnormal liver function tests suggesting liver dysfunction (AST and ALT ≥3 x of the upper limits of normal; total bilirubin ≥2 x the upper limits of normal or >3.0 mg/dl in patients with Gilbert's syndrome).
- 3.1.2.9 Subjects with other medical conditions deemed by the principal investigator (or associates) to make the subject ineligible for protocol procedures.
- 3.1.2.10 Women who are pregnant or breast-feeding. The effects of ferumoxytol on the developing human fetus are unknown. For this reason, women of child-bearing potential and men must agree to use adequate contraception (hormonal or barrier method of birth control; abstinence) prior to study entry and for 1 day after study related imaging is completed. Should a woman become pregnant or suspect she is pregnant while she or her partner is participating in this study, she should inform her treating physician immediately.
- 3.1.3 Inclusion of Women and Minorities

Members of all races and ethnic groups are eligible for this trial. Women are excluded from arm 1 of this trial as prostate cancer does not occur in females.

3.2 Screening Evaluation

Subjects will be seen in the UOB, GMB or ROB clinics by members of each respective team. Conventional imaging (e.g. CT, MRI) confirming presence of prostate or bladder (transitional cell carcinoma) or kidney cancer (all types of renal cell cancer) with evidence of lymph node involvement [with a short axis diameter of \geq 1.5cm measured on conventional CT or MRI] will be reviewed by Molecular Imaging Program Staff.

3.2.1 Screening Test

3.2.1.1 Evaluations:

- History
- Weight
- vital signs (BP, HR, RR, & Temperature)
- clinical laboratory assessments (CBC w/diff, Acute Care Panel, Hepatic Panel, Mineral Panel, serum Iron, ferritin, % saturation transferrin and TIBC).
- Serum or Urine Pregnancy Test in women of reproductive potential

3.3 Registration Procedures

Authorized staff must register an eligible candidate with NCI Central Registration Office (CRO) within 24 hours of signing consent. A registration Eligibility Checklist from the web site (http://home.ccr.cancer.gov/intra/eligibility/welcome.htm) must be completed and sent via encrypted email to: NCI Central Registration Office (HOIS) <ncicentralregistration-[contact]>. After confirmation of eligibility at Central Registration Office, CRO staff will call pharmacy to advise them of the acceptance of the patient on the protocol prior to the release of any investigational agents. Verification of Registration will be forwarded electronically via e-mail to the research team. A recorder is available during non-working hours.

4.2 Ferumoxytol Administration

For all subjects in all three arms, ferumoxytol will be administered at a dose of 7.5mg/kg Fe. Each arm will include 10 evaluable patients.

Ferumoxytol will be administered as an intravenous infusion in 50-200 mL 0.9% Sodium Chloride Injection, USP or 5% Dextrose Injection, USP over at least 15 minutes..

4.3 MRI scan

Prior to entering the scanner the patient will answer the standard MRI safety checklist administered to all patients undergoing MRI in the Clinical Center to insure that it is safe to perform an MRI. The patient will be placed into the magnet in supine position and an intravenous line will be placed. A 32 channel cardiac coil will be used for MR imaging.

The following scans will be obtained:

- Scout view of the target lesion area to check positioning of the phased array cardiac coil.
- Axial T1 weighted MRI of pelvis.
- Axial T2 weighted MRI of pelvis.
- Axial T2* weighted MRI of pelvis.

- Axial diffusion weighted MRI of the pelvis
- Total nominal time: 40 minutes +/- 5 minutes for setup and clean-up +/- 10 minutes in case any sequence needs to be repeated due to unforeseen events such as patient motion during imaging acquisition. At any given time the patient will be required to lie still for 5-7 minutes.

After completion of the pre-infusion MRI scan, the patient will be taken into observation room and Ferumoxytol infusion will be performed as detailed above. The patient will be released after determining vital signs are stable and requested to return for MR imaging at approximately 24 and 48 hours later.

24 hours following the Ferumoxytol infusion, the same MR imaging protocol specified above will be performed with the same MRI set up.

48 hours following the Ferumoxytol infusion, the MR imaging protocol will again be performed with the same MRI set up.

Following imaging acquisition, the data will be transferred to the clinical PACS system for storage.

4.4 Ultrasound

Ultrasound images of the target lymph nodes will be obtained in accessible lymph nodes with 2 different probes (9MHz and 6-15MHz probes) in the same session. Total nominal time for ultrasound imaging is expected to be 10-15 minutes. The same machine (GE LOGIQ E9) will be used for each scan and ultrasound will be performed by the same sonography technician to keep the imaging consistent.

4.5 Procedure Monitoring

The Principal Investigator or other Licensed Independent Practitioner (individual who is licensed to practice independently, i.e. MD, NP, or PA) will be in attendance during infusion. In the event of an emergency such as allergic reaction, emergent treatment will be initiated using emergency medication kits available in Molecular Imaging Clinic. The attending from UOB, ROB, or GMB will be paged [contact]) if needed to treat patient symptoms or for follow up care. In the event the attending is unavailable, [name] should be called [contact]).

Vital signs: Blood pressure, heart rate, respiratory rate, will be taken prior to infusion and every 15 minutes after infusion for 1 hour or until stable. Once stable, patient will be released from Molecular Imaging Clinic.

4.6 Duration of Follow Up

Patients removed from study for unacceptable adverse events will be followed until the resolution or stabilization of the adverse event.

Patients who will undergo biopsy or surgical intervention will remain on study until completion of their surgical procedure or biopsy (core needle biopsy or fine needle aspiration) and analysis of lymph node dissection, at which time they will be removed from study.

Patients who do not undergo biopsy or surgical intervention will have their disease monitored per the protocol they are enrolled in. If the target node is determined to be malignant based on >30% decreases or >20% increases in size then the patient will be removed from the study. In cases when the target node does not change (\leq 30% decrease, \leq 20% increase) then they will be

followed for at least one year. The patient's medical history and imaging studies will be acquired from the patient's medical record, PACs, or their primary care MD. Thus, the patients will remain on study until such time as the nature of their target lymph node can be determined by follow up testing.

In the event that a patient experiences an allergic reaction or toxicity greater than grade 2 during the Ferumoxytol infusion, the infusion will be stopped immediately and standard supportive measures instituted. No further Ferumoxytol will be administered.

4.7 Study Calendar

All efficacy and safety measurements obtained during the course of the study are summarized in the Study Calendar.

	Pre- study	^{a,b} Ultrasound and MR imaging			^{c, d} Surgical procedure/ Core Needle/fine needle aspiration Biopsy	^c Follow up of medical history and conventional imaging studies	
		Just prior to MRI	Pre- infusion MRI scan	24 hour post infusion MRI scan	48 hour post infusion MRI scan	Within 12 weeks following Ferumoxytol enhanced MR imaging	at least 1 year after Ferumoxytol infusion MRI
Pathology report confirming prostate, bladder or kidney cancer	Х					Х	
Informed consent	Х						
Demographics	Х						
Medical history	Х						
CBC w/diff, plts	Х						
Serum chemistry	Х						
Serum Iron, ferritin, % saturation transferrin and TIBC	Х			Х			
Serum or Urine Pregnancy Test	Х	Xe					
Intravenous line started		Х	X				
Ferumoxytol infusion			Х				

Table 1: Study Calendar

	Pre- study	^{a,b} Ultrasound and MR imaging			^{c, d} Surgical procedure/ Core Needle/fine needle aspiration Biopsy	^c Follow up of medical history and conventional imaging studies	
		Just prior to MRI	Pre- infusion MRI scan	24 hour post infusion MRI scan	48 hour post infusion MRI scan	Within 12 weeks following Ferumoxytol enhanced MR imaging	at least 1 year after Ferumoxytol infusion MRI
Vital sign monitoring		Х	Х	Х	Х		

a: Ultrasound and MRI will be done on the same day. For the baseline (pre-infusion) time point, ultrasound will be done before the MRI and for post-infusion 24hr and 48hr time points the sequencing of these studies can change.

b: Intravenous line starting, vital sign monitoring will be done after the MRI scans only, but not after the ultrasound scans.

c: Imaging will be correlated with histology of resected or biopsied lymph nodes when available or patient will be evaluated with clinical assessment and conventional imaging findings (using RECIST criteria), which may be extended up to a period of at least 12 months in cases of stable nodes.

d: Surgical excision or biopsy of the target lymph node will be performed within 12 weeks following the ferumoxytol enhanced MRI.

e: Performed \leq 48 hours prior to infusion of Ferumoxytol for all women of reproductive potential. The test need not be performed if screening test was done within appropriate time frame.

4.8 Surgical Guidelines

As part of their standard of care for their cancer (prostate, bladder or kidney), subjects in each arm may have surgery or a biopsy of the lymph node within 12 weeks following Ferumoxytol enhanced MR imaging. Pathologic specimens will be obtained for histological assessments.

4.9 Criteria for Removal from Study

- If a patient is found to be pregnant after study enrollment but prior to Ferumoxytol infusion
- Patients will be removed from study following prostatectomy or biopsy or after their 1 year clinical assessment. If the patient experiences an AE that prohibits them from completing the Ferumoxytol enhanced MR imaging session they will be taken off-study upon resolution of toxicity. In cases where Ferumoxytol enhanced MR imaging findings indicate possible loco-regional and/or distant metastases, the information will be discussed with the referring physician. Further evaluation with standard of care diagnostic imaging and/or biopsy will be performed at the discretion of the referring physician. The surgical excision or biopsy will be performed only if it is clinically

indicated (standard of care). As the significance of a Ferumoxytol enhanced MR imaging-depicted lesion is uncertain, the decision to pursue pathological confirmation and the methods of doing so will be left to the referring clinician and is not dictated by this imaging protocol.

- A patient may withdraw from the study at any time.
- 4.9.1 Off-Study Procedure

Authorized staff must notify Central Registration Office (CRO) when a subject is taken offstudy. An off-study form from the web site

(http://home.ccr.cancer.gov/intra/eligibility/welcome.htm) main page must be completed and sent via encrypted email to: NCI Central Registration Office (HOIS) <[contact]>.

4.10 Supportive Care Guidelines

In the event that a subject has a reaction (allergic) to Ferumoxytol, all appropriate medical measures will be taken immediately. In rare instances, this may entail admission to the hospital on according to the directions from the referring team.

5 DATA COLLECTION AND EVALUATION

5.1 Data Collection

Data will be collected by the Molecular Imaging Program staff and stored in a passwordprotected file in NCI C3D. The data will be entered at least on a weekly basis.

Data collection will include demographics, the primary tumor diagnosis date, biopsy date, and pathological diagnosis including tumor grade. Monitoring for AEs will be performed from the start of Ferumoxytol infusion until 48 hours post infusion. AEs related to the standard of care prostatectomy or needle biopsy will NOT be collected or reported under this protocol. Raw image data will be stored on a secure external drive. Reconstructed imaging data will include storage of anonymized images from each time point and other extracted image parameters. This will be stored in a secure, password protected imaging database. Post-operative histology data and subsequent correlative analysis will be stored in the password-protected database.

End of study procedures: Data will be stored according to HHS, FDA regulations, and NIH Intramural Records Retention Schedule as applicable.

Loss or destruction of data: Should we become aware that a major breech in our plan to protect subject confidentiality and trial data has occurred, the IRB will be notified.

5.2 Toxicity Criteria

The following adverse event management guidelines are intended to ensure the safety of each patient while on the study. The descriptions and grading scales found in the revised NCI Common Terminology Criteria for Adverse Events (CTCAE) version 4.0 will be utilized for AE reporting. All appropriate treatment areas should have access to a copy of the CTCAE version 4.0. A copy of the CTCAE version 4.0 can be downloaded from the CTEP web site (http://ctep.cancer.gov/protocolDevelopment/electronic_applications/ctc.htm#ctc_40).

5.3 Imaging Interpretation

The location of lymph nodes will be indicated on T1W, T2W and T2*W unenhanced MR images and the size of each node will be measured from the T1 images. Each visualized node will be assigned a number and a site (e.g. right, left, internal, external iliac, right left retroperitoneal). The location of the nodes will be transcribed to a map of the targeted region (chest, abdomen or pelvis). The map, nodal characterizations, and the MR images will be made available to the referring physician for reference. Signal intensity of visualized target lymph node will be recorded on unenhanced and 24 and 48 hours post Ferumoxytol infusion T2*W MR images by placing operator defined region-of-interest. Signal intensity changes will be measured between pre-infusion, 24 and 48 hours post Ferumoxytol infusion MR scans.

For the ultrasound imaging interpretation, the baseline and 24hour, 48hour post-infusion ultrasound images will be visually compared to monitor the signal changes.

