7 STATISTICAL CONSIDERATIONS

7.1 Study Design/Endpoints

- This is an open-label, single-center study. Fifty evaluable subjects in three different arms (30 in arm 1 and 10 in arms 2 and 3) will be enrolled into the study.
- The primary objective is to compare the difference in signal between metastatic and normal nodes in prostate, kidney and bladder cancer patients.
- For determining the difference in signal between metastatic and normal nodes patients will be infused 7.5mg/kg Fe dose of Ferumoxytol.
- Subjects with documented prostate or bladder or kidney cancer will undergo preinfusion and 24, 48 hours post-Ferumoxytol infusion MRI consisting of T1 weighted (W), T2W and T2*W MRI at 3 Tesla (T) magnet.
- The difference in signal between metastatic and normal nodes will be determined by measuring the difference in signal between tumor and normal node, and determining the maximum difference per each imaging time point.
- Patients will also undergo ultrasound examination pre-infusion and 24, 48 hours post-Ferumoxytol infusion time points. The signal changes at post-infusion ultrasound will be visually evaluated in an exploratory manner.

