7.5 Analysis of Secondary Endpoints

The secondary endpoint of this study is to determine the most optimal timing for imaging: 24 hours vs. 48 hours post infusion.

One secondary objective of the study is to determine the most optimal timing for imaging: 24 hours vs. 48 hours post infusion. All the enrolled patients will be imaged at both time points post infusion, and signal change at both time points will be calculated. The time point with larger separation between metastatic and normal nodes with respect to post-infusion signal change will be considered the optimal timing for imaging.

Another second objective of the study is to use an ultrasound scan to evaluate visually (qualitatively) if there is agent uptake. The ultrasound scan will be done before infusion and 24 hours, 48 hours after infusions. This second objective is exploratory, and as such summary statistics such as the proportion of agent take at each time point and the corresponding standard error will be reported. In order to account for the intra-patient correlation of agent uptake of multiple nodes, the linear mixed effects model with the random intercept will be used to estimate the proportion of agent uptake at each time point.

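### Ultrasound uptake is judged visually against a named baseline with no masking to time point described, so an expectation-driven call cannot be told from a real change

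*Combined protocol and SAP*

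**What the plan says.** Ultrasound at pre-infusion, 24 h and 48 h serves a listed secondary objective (Section 1.1.2.2).

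- **Reading.** Section 5.3 says that "the baseline and 24hour, 48hour post-infusion ultrasound images will be visually compared to monitor the signal changes". Section 7.1 adds: "The signal changes at post-infusion ultrasound will be visually evaluated in an exploratory manner".
- **Endpoint.** Section 7.5 states the aim as to "use an ultrasound scan to evaluate visually (qualitatively) if there is agent uptake".
- **Reporting.** Section 7.5 says that "summary statistics such as the proportion of agent take at each time point and the corresponding standard error will be reported". A linear mixed model with a random intercept is to allow for several nodes per patient.
- **Status.** Section 7.5: "This second objective is exploratory".
- **Acquisition.** Section 4.4 limits ultrasound to accessible target nodes, uses one machine and two probes, and says that "ultrasound will be performed by the same sonography technician to keep the imaging consistent".
- **Storage.** Section 5.1 provides for "storage of anonymized images from each time point and other extracted image parameters".

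The supplied text does not say who reads the ultrasound images, in what order, whether the time label is visible, or which appearance counts as uptake.

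**The concern.** The outcome is subjective, and the expected direction of change is obvious to anyone who knows which image was taken before the infusion. Baseline is the named comparator and no masking is described, so the method as written leaves that knowledge open to the reader. Some calls of uptake may then reflect expectation.

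The planned statistics have no way of showing how many. Section 5.4 compares histology with T2*-weighted MRI signal change and does not mention ultrasound. No repeat scan without agent is scheduled. A scored pre-infusion image could act as a reference, but Sections 5.3 and 7.1 suggest that only change after infusion is judged.

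What is at stake is whether the reported proportion can be interpreted. The MRI comparison is not at stake.

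**Working it through.** **The plan's own figure.** None is stated for ultrasound. The only power figure, 93% in Section 7.4, belongs to the MRI primary analysis. A two-sided paired t-test with n = 10, difference 3, SD of the difference 1.7 × √2 = 2.404 and 5% level gives 93.8%, so the stated figure reproduces. It has no bearing on this point.

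**Inputs for an illustration.** All of these are assumptions:
- f, the probability that a node without real change is called as uptake: 0.10 to 0.30.
- Se, the probability that a real change is called: 0.80.
- n, the number of nodes read, one per patient: 30 or 50. Section 7.1 gives 50 evaluable patients and Sections 4.1 and 7.2 give 30. The number with an accessible node is not stated and could be smaller.

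**Step 1: expected reported proportion.** With true uptake proportion π,

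q = π × Se + (1 − π) × f.

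If the agent has no sonographic effect, π = 0 and q = f. The output is simply the assumed rate, so this step shows the mechanism and does not estimate its size.

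**Step 2: standard error when π = 0**, from √(f(1 − f)/n):

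| f | n = 30 | n = 50 |
|---|---|---|
| 0.10 | 0.055 | 0.042 |
| 0.20 | 0.073 | 0.057 |
| 0.30 | 0.084 | 0.065 |

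For example, f = 0.20 with n = 50 gives 10 expected false calls. Ten calls in 50 have an exact 95% interval of about 10% to 34%. That interval excludes zero although nothing happened.

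**Step 3: can the planned statistics reveal f?** Take two cases with Se = 0.80:
- π = 0.50, f = 0.10: q = 0.50 × 0.80 + 0.50 × 0.10 = 0.45.
- π = 0.30, f = 0.30: q = 0.30 × 0.80 + 0.70 × 0.30 = 0.45.

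The reported proportion and its standard error are the same in both. The random intercept handles correlation between nodes of one patient, so it does not help here.

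**Step 4: effect of time-masked scoring.** If the agent does nothing and the reader cannot tell the time points apart, each image of a node has the same chance of being scored positive. The expected 24 h or 48 h difference from pre-infusion is then 0 instead of f. Treating the two sets of scores as independent, the standard error of the difference is √(2f(1 − f)/n), where f now stands for the background rate. At f = 0.10 it is 0.077 (n = 30) or 0.060 (n = 50). At f = 0.20 it is 0.103 or 0.080. Positive correlation between images of the same node would lower these values.

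**The case against.** - **Reader knowledge of time is inferred.** This is correct. No section says that the reader knows it, and the statement "This is an open-label, single-center study" concerns treatment, not image reading. What stands is that baseline is the named comparator and no masking is described.
- **A built-in 0% before infusion.** A reader might infer that the pre-infusion proportion is zero by construction. The documents do not settle this. Section 7.5 lists the pre-infusion scan and then reports each time point, which could mean that the pre-infusion image is scored and a partial reference exists. Sections 5.3 and 7.1 point the other way. The plan is unclear, and the claim of a built-in zero is too strong.
- **Acquisition is standardized.** The same machine and technician limit scan-to-scan variation. They do not control the reading.
- **Images are anonymized.** Section 5.1 keeps them by time point and does not say that the time label is hidden from the reader.
- **Scoring images singly changes the question.** This objection has force. A proportion from images rated alone is the background frequency of an appearance, not the false-positive rate of a change call, and giving up the paired view may cost sensitivity. Isolated rating should therefore not be required.
- **It is exploratory.** True. No test, threshold or decision rests on it, and Section 7.5 does not restrict the output to a proportion and standard error. This limits the importance of the point but does not make the proportion interpretable.

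**Conclusion.** The concern holds in limited form. Ultrasound uptake is a visual call against a named baseline, with no masking, reading order, positive criterion or no-agent reference described, and the planned summary statistics cannot separate expectation from real change.

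The size is unknown. The 10-30% range, the sensitivity of 0.80 and the node counts are assumptions, and nothing in the documents shows that false calls would be that frequent. A reader might conclude that any reported uptake of 10-30% would be spurious; the documents do not support that.

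The point affects one exploratory secondary objective and leaves the MRI primary analysis and its power untouched. It is a cheap improvement and not a defect that threatens the trial.

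**What to change.** Add to Sections 5.3 and 7.5:

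1. State who reads the ultrasound images and the one sonographic feature that is scored.
2. The same reader scores the stored images of each node at all three time points, pre-infusion included, with time labels removed and in random order. Images of one node may be viewed together as long as their order is masked.
3. Report the pre-infusion proportion as the background rate of the feature, and 24 h and 48 h as within-node differences from it, allowing for clustering by patient.
4. An unmasked side-by-side read may be kept as a supplement, labelled as such.

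**Cost.** No extra scan, patient or reader is needed. There is some preparation time, reading waits until the 48 h images are stored, and some sensitivity to subtle change may be lost. A difference can also be less precise than a raw proportion: at f = 0.10 and n = 30 the standard error is 0.077 instead of 0.055 if the scores are independent. Masking removes expectation about time. Ordinary variation in gain or angle remains, but it then enters the background rate as well as the later readings.
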